8.2.1.1. Hgb Stopping Criteria

GSK will supply a point-of-care Hgb analyzer (HemoCue) to each site for rapid and convenient monitoring of Hgb levels and to ensure consistency of Hgb measurements across sites participating in the study.

Blood samples for measurement of Hgb concentrations via HemoCue will be collected and recorded in the eCRF. [Table 3](#) summarizes the Hgb values and corresponding action to be taken at each visit.

Table 3 Hgb Stopping Criteria

Hgb (g/dL) at visit		Action
<7.5		Repeat HemoCue assessment on the same sample at same study visit to confirm; take average of 2 values. If confirmed, permanently discontinue study treatment and withdraw participant from the study.
≥7.5 - <13.0 With:	≥2.0 g/dL decrease in Hgb over the previous 2 weeks	Repeat HemoCue assessment on the same sample at same study visit to confirm; take average of 2 values. If confirmed, permanently discontinue study treatment and withdraw participant from the study.
≥7.5 - <13.0 With:	<1.0 absolute change in Hgb over the previous 2 weeks	Continue study treatment.
≥7.5 - <13.0 With:	≥1.0 increase in Hgb over the previous 2 weeks	Repeat HemoCue assessment on the same sample at same study visit to confirm; take average of 2 values. If confirmed, permanently discontinue study treatment and withdraw participant from the study.
≥13.0		Repeat HemoCue assessment on the same sample at same study visit to confirm; take average of 2 values. If confirmed, permanently discontinue study treatment and withdraw participant from the study.

8.2.1.2. Iron Stopping Criteria

Participants must remain iron replete throughout the study, and should remain on their regular oral iron supplement as described in Section 7.7.1.

Based on the PI's clinical judgement in consultation with Medical Monitor, if the subject cannot be maintained on the same oral iron dose during the study treatment periods, the subject must be withdrawn.

8.3. Lost to Follow Up

A participant will be considered lost to follow-up if he or she repeatedly fails to return for scheduled visits and is unable to be contacted by the study site.

The following actions must be taken if a participant fails to return to the clinic for a required study visit:

- The site must attempt to contact the participant and reschedule the missed visit as soon as possible and counsel the participant on the importance of maintaining the assigned visit schedule and ascertain whether or not the participant wishes to and/or should continue in the study.
- Before a participant is deemed lost to follow up, the investigator or designee must make every effort to regain contact with the participant (where possible, 3 telephone calls and, if necessary, a certified letter to the participant's last known

mailing address or local equivalent methods). These contact attempts should be documented in the participant's medical record.

- Should the participant continue to be unreachable, he/she will be considered to have withdrawn from the study with a primary reason of lost to follow-up.

9. STUDY ASSESSMENTS AND PROCEDURES

- Study procedures and their timing are summarized in the SoA (Section 2).
- Protocol waivers or exemptions are not allowed.
- Immediate safety concerns should be discussed with the sponsor immediately upon occurrence or awareness to determine if the participant should continue or discontinue study treatment.
- Adherence to the study design requirements, including those specified in the SoA, is essential and required for study conduct.
- All screening evaluations must be completed and reviewed to confirm that potential participants meet all eligibility criteria. The investigator will maintain a screening log to record details of all participants screened and to confirm eligibility or record reasons for screening failure, as applicable.
- Procedures conducted as part of the participant's routine clinical management (e.g., Hgb levels) and obtained before signing of ICF may be utilized for screening or baseline purposes provided the procedure met the protocol-specified criteria and was performed within the time frame defined in the SoA (Section 2).
- The maximum amount of blood collected from each participant over the duration of the study, including any extra assessments that may be required, will not exceed 500 mL.
- Repeat or unscheduled samples may be taken for safety reasons or for technical issues with the samples.

9.1. Efficacy Assessments

Efficacy is not evaluated in this study.

9.2. Adverse Events

The definitions of an AE or SAE can be found in [Appendix 6](#).

AEs will be reported by the participant (or, when appropriate, by a caregiver, surrogate, or the participant's legally authorized representative).

The investigator and any designees are responsible for detecting, documenting, and reporting events that meet the definition of an AE or SAE and remain responsible for following up AEs that are serious, considered related to the study treatment or the study, or that caused the participant to discontinue the study treatment (see Section 8).

9.2.1. Time Period and Frequency for Collecting AE and SAE Information

- All SAEs will be collected from the start of treatment until the follow-up visit at the time points specified in the SoA (Section 2). However, any SAEs assessed as related to study participation (e.g., study treatment, protocol-mandated procedures, invasive tests, or change in existing therapy) or related to a GSK product will be recorded from the time a subject consents to participate in the study.
- All AEs will be collected from the start of treatment until the follow-up visit at the time points specified in the SoA (Section 2).
- Medical occurrences that begin before the start of study treatment but after obtaining informed consent will be recorded on the Medical History/Current Medical Conditions section of the eCRF not the AE section.
- All SAEs will be recorded and reported to the sponsor or designee immediately and under no circumstance should this exceed 24 hours, as indicated in [Appendix 6](#). The investigator will submit any updated SAE data to the sponsor within 24 hours of it being available.
- Investigators are not obligated to actively seek AEs or SAEs in former study participants. However, if the investigator learns of any SAE, including a death, at any time after a participant has been discharged from the study, and he/she considers the event to be reasonably related to the study treatment or study participation, the investigator must promptly notify the sponsor.
- The method of recording, evaluating, and assessing causality of AEs and SAEs and the procedures for completing and transmitting SAE reports are provided in [Appendix 6](#).

9.2.2. Method of Detecting AEs and SAEs

Care will be taken not to introduce bias when detecting AE and/or SAE. Open-ended and non-leading verbal questioning of the participant is the preferred method to inquire about AE occurrence.

9.2.3. Follow-up of AEs and SAEs

After the initial AE/SAE report, the investigator is required to proactively follow each participant at subsequent visits/contacts. All SAEs, and non serious AEs of special interest (as defined in Section 9.2.4), will be followed until the event is resolved, stabilized, otherwise explained, or the participant is lost to follow-up (as defined in Section 8.3). Further information on follow-up procedures is given in [Appendix 6](#).

9.2.4. Adverse Events of Special Interest (AESI)

Adverse Events of Special Interest (AESI) have been identified based on non-clinical studies with daprodustat, clinical experience with rhEPOs, and current information regarding HIF-regulated pathways in mediating hypoxia-associated pathophysiology. The currently identified AESI for daprodustat are as follows:

- Thrombosis and/or tissue ischemia secondary to excessive erythropoiesis
- Death, MI, stroke, heart failure, venous thromboembolism, thrombosis of vascular access
- Cardiomyopathy
- Pulmonary artery hypertension
- Cancer-related mortality and tumor progression and recurrence
- Esophageal and gastric erosions
- Proliferative retinopathy, macular edema, choroidal neovascularization
- Exacerbation of rheumatoid arthritis
- Worsening of hypertension

9.2.5. Regulatory Reporting Requirements for SAEs

- Prompt notification by the investigator to the sponsor of a SAE is essential so that legal obligations and ethical responsibilities towards the safety of participants and the safety of a study treatment under clinical investigation are met.
- The sponsor has a legal responsibility to notify both the local regulatory authority and other regulatory agencies about the safety of a study treatment under clinical investigation. The sponsor will comply with country-specific regulatory requirements relating to safety reporting to the regulatory authority, Institutional Review Boards (IRB)/Independent Ethics Committees (IEC), and investigators.
- Investigator safety reports must be prepared for suspected unexpected serious adverse reactions (SUSAR) according to local regulatory requirements and sponsor policy and forwarded to investigators as necessary.
- An investigator who receives an investigator safety report describing a SAE or other specific safety information (e.g., summary or listing of SAE) from the sponsor will review and then file it along with the IB and will notify the IRB/IEC, if appropriate according to local requirements.

9.2.6. Cardiovascular and Death Events

For any cardiovascular events listed below and all deaths, whether or not they are considered SAEs, specific Cardiovascular (CV) and Death sections of the eCRF will be required to be completed. These sections include questions regarding cardiovascular (including sudden cardiac death) and non-cardiovascular death.

- Myocardial infarction/unstable angina
- Congestive heart failure
- Arrhythmias
- Valvulopathy
- Pulmonary hypertension

- Cerebrovascular events/stroke and transient ischemic attack
- Peripheral arterial thromboembolism
- Deep venous thrombosis/pulmonary embolism
- Revascularization

The CV eCRFs are presented as queries in response to reporting of certain CV MedDRA terms. The CV information should be recorded in the specific cardiovascular section of the eCRF within one week of receipt of a CV Event data query prompting its completion.

The Death eCRF is provided immediately after the occurrence or outcome of death is reported. Initial and follow-up reports regarding death must be completed within one week of when the death is reported.

9.2.7. Possible Suicidality Related Adverse Events

If during the study there is an occurrence of an AE or SAE which in the investigator's opinion is possibly related to suicidality, the Possible Suicidality Related Adverse Events (PSRAE) eCRF form should be completed (in addition to the AE and SAE pages, as appropriate).

This event may include, but is not limited to, one that involves suicidal ideation, a preparatory act toward imminent suicidal behavior, a suicide attempt, or a completed suicide. The investigator will exercise his or her medical and scientific judgment in deciding whether an event is possibly related to suicidality.

9.2.8. Pregnancy

- Details of all pregnancies in female participants and the outcome for the neonate, if applicable, will be collected from the start of study treatment.
- If a pregnancy is reported, the investigator should inform GSK within 24 hours of learning of the pregnancy and should follow the procedures outlined in [Appendix 7](#).
- Abnormal pregnancy outcomes (e.g., spontaneous abortion, fetal death, stillbirth, congenital anomalies, ectopic pregnancy) are considered SAE.

9.3. Treatment of Overdose

For this study, any dose of daprodustat greater than 4 mg within a 24-hour time period will be considered an overdose.

There is no specific antidote for overdose with daprodustat. The expected manifestations of daprodustat overdosage include signs and symptoms associated with an excessive and/or rapid increase in Hgb concentration. In the event of a suspected overdose, it is recommended that the appropriate supportive clinical care be instituted, as dictated by the participant's clinical status. Additionally, participants should be monitored closely for CV events, increased heart rate and hematologic abnormalities.

9.4. Safety Assessments

Planned time points for all safety assessments are provided in the SoA (Section 2).

9.4.1. Entry Criteria

Entry criteria are to be assessed during the screening period, at Week -4, Week -2 and Day 1. The timing for assessment of specific criteria are detailed in the SoA (Section 2), and are described in [Table 4](#)

Table 4 Timing of Entry Criteria Assessments

Timing	Procedures
Week -4	Informed consent, complete physical examination, medical history, demography, height, weight, vital signs, clinical safety laboratory assessments, pregnancy test, eGFR, Hgb, HIV, concomitant medications, rhEPO dose
Week -2	Brief physical examination, Hgb, estradiol & FSH (as needed), ECG, folate, Vitamin B ₁₂ , hsCRP, ferritin, TSAT, concomitant medications, rhEPO dose
Day 1	Brief physical examination, weight, vital signs, Hgb, pregnancy test, concomitant medications, rhEPO dose

9.4.2. Physical Examinations

- A complete physical examination will include, at a minimum, assessments of the skin, cardiovascular, respiratory, gastrointestinal and neurological systems. Height and weight will also be measured and recorded.
- A brief physical examination will include, at a minimum, assessments of the skin, lungs, cardiovascular system, and abdomen (liver and spleen).
- Investigators should pay special attention to clinical signs related to previous serious illnesses.

9.4.3. Vital Signs

- Oral temperature, pulse, respiratory rate, and blood pressure will be assessed.
- Blood pressure and pulse measurements will be assessed in a seated position with a completely automated device. Manual techniques will be used only if an automated device is not available.
- Blood pressure and pulse measurements should be preceded by at least 5 minutes of rest for the participant in a quiet setting without distractions (e.g., television, cell phones).
- Vital signs (to be taken before blood collection for laboratory tests) will consist of 1 pulse and 3 blood pressure measurements (3 consecutive blood pressure

readings will be recorded at intervals of at least 1 minute). The average of the 3 blood pressure readings will be recorded on the eCRF.

9.4.4. Electrocardiograms

- ECG measurements will be obtained as outlined in the SoA (Section 2). Full 12-lead ECGs will be recorded with the participant in a supine position. Heart rate, PR interval, QRS duration, and QT (uncorrected) interval will be measured. QTcB will be calculated (machine read or manually).
- At each time point at which ECGs are required, two additional ECGs are required if the initial ECG measurement indicates prolonged QTc (see Section 6.1) using the automated or manually calculated QTcB value. The average QTcB value of all three ECGs will be used to determine eligibility.

9.4.5. Clinical Laboratory Assessments

Refer to [Appendix 4](#) for the list of protocol-required clinical chemistry and hematology ([Table 8](#)) and additional clinical laboratory assessments ([Table 9](#)) to be performed and to the SoA (Section 2) for the timing and frequency.

- The investigator must review the laboratory report, document this review, and record any clinically relevant changes occurring during the study in the AE section of the eCRF. The laboratory reports must be filed with the source documents. Clinically significant abnormal laboratory findings are those which are not associated with the underlying disease, unless judged by the investigator to be more severe than expected for the participant's condition.
- All laboratory tests with values considered clinically significantly abnormal during participation in the study or within 48 hours after the last dose of study treatment should be repeated until the values return to normal or baseline or are no longer considered significantly abnormal by the investigator or medical monitor.
- If such values do not return to normal/baseline within a period of time judged reasonable by the investigator, the etiology should be identified and the sponsor notified.
- All protocol-required laboratory assessments, as defined in [Appendix 4](#), must be conducted in accordance with the laboratory manual and the SoA.

9.4.6. Liver Chemistry Monitoring

Clinical laboratory assessments for liver chemistry monitoring include ALT, AST, bilirubin and alkaline phosphatase. Refer to the SoA (Section 2) for the frequency of monitoring. Additionally, all of these tests are also part of the Clinical Chemistry Assessments and will be performed at the timepoints where those assessments are done. These assessments must be conducted in accordance with the laboratory manual.

9.5. Pharmacokinetics

Pharmacokinetic (PK) parameters are not evaluated in this study.

9.6. Pharmacodynamics

Pharmacodynamics (PD) are not evaluated in this study.

9.7. Genetics

A blood sample for DNA isolation will be collected from participants who have consented to participate in the genetics analysis component of the study. Participation is optional. Participants who do not wish to participate in the genetic research may still participate in the study.

In the event of DNA extraction failure, a replacement genetic blood sample may be requested from the participant. Signed informed consent will be required to obtain a replacement sample unless it was included in the original consent.

See [Appendix 8](#) for information regarding genetic research. Details on processes for collection and shipment and destruction of these samples can be found in the SRM.

9.8. Biomarkers

9.8.1. Fractional oral iron absorption

Venous blood samples will be collected for measurement of erythrocyte iron content at the times specified in the SoA (Section 2). Further details for blood collection procedures can be found in the SRM. Calculations for fractional iron absorption will be included in the Reporting and Analysis Plan (RAP).

9.8.2. Iron status markers

Markers of iron status (i.e., serum iron, transferrin, TSAT, soluble transferrin receptor, ferritin, hepcidin and erythroferrone) will be assessed at the times listed in the SoA. Measurement of erythroferrone is dependent upon availability of a suitable assay methodology, so may not be assessed. All blood samples for iron status markers to be taken pre dose. Further details for blood collection procedures can be found in the SRM.

9.8.3. Indices of erythropoiesis

Indices of erythropoiesis (i.e., Hgb, hematocrit, red blood cell number, mean corpuscular volume, reticulocyte Hgb and reticulocyte number) are planned to be assessed at the times listed in the SoA (Section 2). Further details for blood collection procedures can be found in the SRM.

9.9. Health Economics OR Medical Resource Utilization and Health Economics

Health Economics/Medical Resource Utilization and Health Economics parameters are not evaluated in this study.

10. STATISTICAL CONSIDERATIONS

10.1. Hypotheses

The primary analysis will test whether daprodustat is superior to rhEPO (i.e., epoetin alfa or darbepoetin alfa) according to the following statistical hypotheses:

Null: The difference in fractional iron absorption between treatment arms (daprodustat-rhEPO (i.e., epoetin alfa or darbepoetin alfa)) is equal to zero.

Alternative: The difference in fractional iron absorption between treatment arms (daprodustat-rhEPO (i.e., epoetin alfa or darbepoetin alfa)) is not equal to zero.

10.2. Sample Size Determination

Sufficient participants will be enrolled such that at least 12 participants comprise the Evaluable Population (See Section 10.3.1.3).

A sample size of 12 participants provides 90% power to detect a paired mean difference of 11% between the two treatment groups under an assumed between-participant standard deviation (SD) of 10.7%. Note this is a conservative estimate of the SD of the paired differences as it is based on a parallel design study (Young, 2009).

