10.2.1. Sample Size Sensitivity

Table 5 illustrates the impact on power for the primary efficacy analysis based on alternative assumptions for the between participant SD and the expected difference between the treatment groups.

Table 5 Impact on power based on alternative assumptions for the between participant SD and the expected difference between the treatment groups

Between participant SD (%)	Expected difference between treatments in Fractional Iron Absorption (%) (daprodustat – rhEPO (i.e., epoetin alfa or darbepoetin alfa))				
	7	9	11	13	15
7	88%	98%	>99%	>99%	>99%
9	69%	88%	97%	>99%	>99%
10.7	54%	76%	90%	97%	>99%
12	43%	66%	82%	93%	98%
14	35%	53%	70%	83%	92%

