4.2.2. Main analytical approach

Endpoint / Variables

 Fractional oral iron absorption (%)
Model Specification

 To compare daprodustat to rhEPO on fractional iron absorption, a mixed effects model will be fitted Terms fitted in the mixed effect model will include:

Endpoint / Variables

 • Fixed effect: treatment, period, and iron isotope • Random effect: participant • The Kenward and Roger method for approximating the denominator degrees of freedom and correcting for bias in the estimated variance-covariance of the fixed effects will be used. • Using PROC MIXED in SAS, the covariance for the random participant effect (G matrix) will be fit using an unstructured covariance structure by specifying ‘type=UN’ on the RANDOM line. 
 • In the event that this model fails to converge, alternative covariance structures may be considered such as Variance Components or Compound Symmetry. • Akaike’s Information Criteria (AIC) will be used to assist with the selection of covariance structure.
Model Checking & Diagnostics

 • For the Mixed Model, model assumptions will be checked, and appropriate adjustments may be applied based on the data. • Distributional assumptions underlying the model used for analysis will be examined by obtaining a normal probability plot of the residuals and a plot of the residuals versus the fitted values (i.e. checking the normality assumption and constant variance assumption of the model respectively) to gain confidence that the model assumptions are reasonable. • If there are any departures from the distributional assumptions, alternative transformations, such as data squared or square root of data, will be explored. • Non-parametric analyses will be conducted if the normality assumption does not hold.
Model Results Presentation

Fractional oral iron absorption will be summarized using n, mean, SD, median, minimum, and maximum.
 
Point estimates, corresponding 95% confidence intervals, and two-sided p-values will be constructed for the comparison of efficacy of daprodustat to rhEPO.

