5. SAMPLE SIZE DETERMINATION

Sufficient participants will be enrolled such that at least 12 participants comprise the Evaluable Population. A sample size of 12 participants provides 90% power to detect a paired mean difference in fractional iron absorption of 11% between the two treatment groups under an assumed between-participant standard deviation (SD) of 10.7%. Note this is a conservative estimate of the SD of the paired differences as it is based on a parallel design study ([Young, 2009](#)). No sample size re-estimation will be performed.

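### The 90% power and Table 5 are paired t-test values with 11 df; the planned model leaves 9 df (about 88.5%), and one Table 5 cell is a separate slip

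*Protocol*

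**What the plan says.** Protocol 10.2 requires that "at least 12 participants comprise the Evaluable Population" and states that "A sample size of 12 participants provides 90% power to detect a paired mean difference of 11% between the two treatment groups". The SD entered is 10.7%, labelled as a between-participant value, and the section says how it is used: "Note this is a conservative estimate of the SD of the paired differences as it is based on a parallel design study". SAP 5 carries the statement over: "A sample size of 12 participants provides 90% power to detect a paired mean difference in fractional iron absorption of 11" percent. Neither section names the test, the significance level or the degrees of freedom.

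Protocol 10.2.1 adds Table 5, titled "Impact on power based on alternative assumptions for the between participant SD and the expected difference between the treatment groups". The sentence introducing it describes the figures as power for the primary efficacy analysis.

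That analysis is set out in Protocol 10.4.1 and SAP 4.2.2. The SAP's terms are "Fixed effect: treatment, period, and iron isotope", with a random participant effect and Kenward-Roger degrees of freedom. The protocol model also has a sequence term, which SAP 4.5 removes. Protocol Table 1 has four sequences with three participants in each.

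**The concern.** The sample size text speaks of a paired difference, and its figures behave like those of a one-sample t-test on 12 differences. The planned model takes treatment, period and isotope from the same 12 within-participant contrasts, so it has fewer error degrees of freedom than that test. If so, the power quoted in both documents is not the power of the analysis that will be run, and nearly every cell of Table 5 is a little too favourable. One cell also looked out of line with its neighbours. At stake is the accuracy of a headline figure and a sensitivity table, not the design.

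**Working it through.** **Inputs.** n = 12 evaluable participants, difference 11 points, SD of differences 10.7 points (Protocol 10.2, SAP 5). The sample size text gives no alpha; two-sided 0.05 is inferred from the two-sided hypothesis (Protocol 10.1) and from the 95% confidence intervals and two-sided p-values in SAP 4.2.2.

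**Formula.** Noncentrality λ = (difference / SD) × √n. Power = P(|T| > t(0.975, df)), where T is noncentral t with df degrees of freedom and noncentrality λ.

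**1. The stated figure.** λ = (11 / 10.7) × √12 = 3.561. With df = 12 − 1 = 11 the critical value is 2.201 and power is 89.9%, so the stated 90% reproduces. Other bases do not give it: the normal approximation gives 94.5%, a one-sided 0.05 test 95.4%, and n = 11 gives 86.6%.

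**2. Error df of the planned model.** There are 24 observations. Participant effects use 12 df, and treatment, period and isotope use 3, so the design matrix has rank 15 and 24 − 15 = 9 df remain. The protocol's sequence term is a between-participant term and does not change this. With three participants per sequence, treatment is orthogonal to period and isotope (the off-diagonal terms of the inverse cross-product matrix are zero). The variance of the treatment contrast is therefore unchanged, and only df are lost.

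**3. Power of the planned model.** λ stays at 3.561. With 9 df the critical value is 2.262 and power is 88.5%; a simulation of the fit gave 88.7%. Solving for 90% power gives a detectable difference of 11.02 points with 11 df and 11.28 points with 9 df.

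**4. Table 5.** Power in %, differences 7 / 9 / 11 / 13 / 15:

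| SD | Printed | 11 df | 9 df |
|---|---|---|---|
| 7 | 88 / 98 / >99 / >99 / >99 | 88.3 / 98.1 / 99.9 / 100 / 100 | 86.8 / 97.6 / 99.8 / 100 / 100 |
| 9 | 69 / 88 / 97 / >99 / >99 | 69.0 / 88.3 / 97.0 / 99.5 / 99.9 | 67.0 / 86.8 / 96.3 / 99.3 / 99.9 |
| 10.7 | 54 / 76 / 90 / 97 / >99 | 54.3 / 75.6 / 89.9 / 96.9 / 99.3 | 52.5 / 73.7 / 88.5 / 96.2 / 99.0 |
| 12 | **43** / 66 / 82 / 93 / 98 | **45.4** / 65.8 / 82.4 / 92.6 / 97.6 | **43.9** / 63.9 / 80.6 / 91.5 / 97.0 |
| 14 | 35 / 53 / 70 / 83 / 92 | 35.3 / 52.8 / 69.8 / 83.3 / 92.1 | 34.1 / 51.1 / 67.9 / 81.6 / 90.9 |

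The 11-df column agrees with 24 of the 25 printed cells. The exception is SD 12 with difference 7, where λ = (7 / 12) × √12 = 2.021 and power is 45.4%, against 43% printed. Moving from 11 to 9 df lowers any cell by at most about 1.9 points (for example SD 9, difference 7: 68.95 − 67.03 = 1.92).

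**The case against.** The strongest reply is that the headline figure is not an arithmetic error. It reproduces for the paired difference that the text names, and sizing a two-period crossover on a paired t-test is a common simplification. The 1.5-point gap is also small beside the uncertainty in the SD. With 9 df, an SD of 10.4 instead of 10.7 already gives 90.2%, and the difference-11 column of Table 5 runs from 70% to above 99%. Twelve is a minimum, and 13 evaluable participants would give 91.5% under the planned model (10 df). The 9 df are conditional too, because SAP 4.2.2 allows other covariance structures, transformations and non-parametric analysis.

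Most of this stands, and it limits the point to a correction of reporting. It does not remove the mismatch: Table 5 is offered as power for the primary efficacy analysis, and its figures belong to a simpler test.

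A reader might infer that the trial is underpowered or needs more participants. The documents do not support that: at the stated alternative, the loss is 1.5 points. A reader might also infer from the 43% cell that Table 5 mixes two bases, since 43.9% with 9 df is close to it. The rest of its row rules this out: 66 / 82 / 93 / 98 are 11-df values, whereas 9 df would give 64 / 81 / 91 / 97. The cell is an isolated slip, and it understates power.

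Whether a between-participant SD is conservative as the SD of differences is a separate and larger question. If the SD of differences were 10.7 × √2 (zero within-participant correlation), power would be about 63% with 11 df. The present point takes 10.7 as given.

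**Conclusion.** The point holds as a small overstatement. Taking the 10.7-point SD of differences as given, with two-sided alpha 0.05, the planned analysis has about 88.5% power at 11 points, against 90% stated. Its 90% detectable difference is about 11.3 points, against 11 stated. The 9 df behind these figures assume 12 balanced completers, a positive estimate of the participant variance and the untransformed mixed model. The 43% cell is wrong on the table's own basis by 45.4 − 43 = 2.4 points. It plays no part in the sizing. Neither matter affects the design, the sample size or the planned analysis.

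**What to change.** In Protocol 10.2 and SAP 5, name the test, alpha and df. Then either restate power as about 88.5% with 9 error df, or keep 90% and give the detectable difference as 11.3 points. Recompute Table 5 on that one basis, as in the 9-df column above, where the SD 12, difference 7 cell becomes 44%. If the paired t-test basis is kept, say so in the text and at minimum correct that cell from 43% to 45%.

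The cost is one sentence in each document and one table. The downside is a stated power 1 to 2 points lower.
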